12.4.4 Handling of missing values not related to intercurrent event

Patients with missing PCR evaluations at 48 weeks will be considered as non-responders. However, if the 48-week PCR evaluation is missing, but both a PCR evaluation at 36 weeks and a PCR evaluation at 60 weeks indicate MMR, the 48-week assessment is imputed as a 'Response', assuming that MMR is maintained between 36 and 60 weeks.

12.4.5 Sensitivity analyses

The hypothetical strategy of handling intercurrent events in [Section 12.4.4](#) is based on missing completely at random (MCAR) assumption. To explore the robustness of analysis, sensitivity analyses exploring different assumptions will be performed. The details will be provided in SAP.

In addition, due to the COVID-19 (Coronavirus) pandemic, there is a risk that planned visits are cancelled, potentially resulting in missing PCR evaluations. The impact of COVID-19 (including potential missing data or having clinic visits replaced by home nursing staff visit to the participant's home) on the primary endpoint will also be analyzed if sufficient (to be detailed in SAP) number of patients are affected.

12.4.6 Supplementary analysis

Subgroup analyses of the primary efficacy endpoint to assess the homogeneity of the treatment effect across demographic and baseline disease characteristics may be conducted on the following subgroups, if there are enough patients in each category:

- Gender: Male and Female
- Race: Asian, Caucasian, or others
- Age at baseline (≥ 18 -< 65 years, ≥ 65 years, ≥ 75 years)
- Reason for discontinuation of the last prior TKI: Warning or failure (i.e. lack of efficacy) or intolerance (i.e. adverse event, lack of tolerability) to the most recent TKI therapy at the time of screening

Note: Only one reason for discontinuation is allowed for each prior therapy.

- Number of prior TKI therapies: 2, 3 or ≥ 4
- Cytogenetic response status at baseline
- Prior TKI treatment
- Prior ponatinib: Yes or No
- Mutation status at baseline: Wild type or mutant

Other subgroup as appropriate, may be analyzed and described in Statistical Analysis Plan (SAP).

12.5 Analysis supporting secondary objectives

The secondary objectives in this study are as follows:

- To evaluate the safety and tolerability of asciminib in patients with CML-CP following two or more prior TKI treatments.
- To assess the rate of MMR in patients with no evidence of MMR at baseline, at alternative time points at weeks 12, 24, 36, 72, 96 and 144.
- To assess the rate of MMR at week 48 for patients with MMR at baseline
- To assess the time to MMR
- To assess the rate of early responses of BCR-ABL1 $\leq 10\%$ and $\leq 1\%$ IS at weeks 12, 24, 36 and 48
- To assess the rate of deep molecular responses (MR4 and MR4.5) at weeks 12, 24, 36, 48, 72, 96 and 144.
- To assess cytogenetic response (% Ph⁺ metaphases) at weeks 48 and EOT.
- To characterize the impact of additional cytogenetic abnormalities on efficacy
- To assess cumulative molecular responses by all-time points.

- To assess duration of MMR.
- To assess sustained deep molecular responses as prerequisite for TFR.
- To assess rate of progression (PFS).
- To assess overall survival (OS).
- To assess time to treatment failure (TTF).
- To evaluate patient reported outcomes and quality of life by using QoL scales.

12.5.1 Efficacy and/or Pharmacodynamic endpoint(s)

Unless otherwise stated the FAS will be used for the analysis of all secondary efficacy endpoints.

No statistical testing of secondary efficacy endpoints will be performed.

- Molecular Response MMR rate at weeks 12, 24, 36, 72, 96 and 144
- MMR rate at week 48 for patients with MMR at baseline
- Rate of MR4 and MR4.5 at weeks 12, 24, 36, 48, 72, 96 and 144
- Rate of BCR-ABL1 $\leq 10\%$ and $\leq 1\%$ at Weeks 12, 24, 36 and 48
- Rate of BCR-ABL1 $\leq 10\%$, BCR-ABL1 $\leq 1\%$, MMR, MR4 and MR4.5 by all-time points

For each endpoint above, the rate and the associated 95% confidence interval based on the Pearson-Clopper method will be presented.

Additional chromosomal abnormalities and occurrence of high-risk ACAs will be analyzed.

The details will be provided in SAP.

Duration of MMR is defined in [Section 8.3.1.1](#) as the time from the date of first documented MMR to the earliest date of loss of MMR, progression to AP or BC, or CML-related death. The time will be censored at the last molecular assessment (PCR) date while on treatment for patients who have not experienced any of the above events.

Duration of MMR will be analyzed by K-M method and presented by K-M plots. The estimated rates of patients who are still responding at various time points will also be provided using K-M method.

Duration of MR4 without loss of MMR will be analyzed in a similar fashion to the analysis of duration of MMR.

The cumulative incidence of MMR will be graphically displayed by an increasing step function. This curve will increase each time (after randomization) at which a new responder is observed and thus will increase up to the best observed response rate (e.g. up to 50% if half of the patients in the analysis population are able to achieve response).

The additional patients who were intolerant to the last TKI and were in MMR already at baseline will be assessed for the duration of MMR using FAS 2.

Time to MMR is defined in [Section 8.3.1.1](#) and calculated as: date of first documented MMR - date of randomization +1. Descriptive statistics (minimum, maximum, median, quartiles, mean, SD) of time to MMR will be provided.

Cytogenetic Response

Patients in FAS will be categorized with counts and percentages provided for cytogenetic response at week 48 and EOT. Shift tables will also be employed to examine the changes in cytogenetic response category from baseline.

CCyR rates at Weeks 48 and EOT and the associated 95% confidence intervals based on the Pearson-Clopper method will be presented.

Treatment failure, disease progression and survival

Progression-Free-Survival (PFS) is defined as the time from the date of randomization to the earliest occurrence of documented disease progression to AP/BC or the date of death from any cause before the cut-off date.

The time will be censored at the date of last study assessment (PCR, cytogenetic, hematologic or extramedullary) or last post-treatment follow-up for patients without event.

Overall survival (OS) is defined as the time from the date of randomization to the date of death. Patients who are alive at the time of the analysis data cutoff date will be censored at the date of last contact before the cut-off date.

Time to treatment failure (TTF) is defined as the time from date of randomization to an event of treatment failure define as BCR-ABL1 > 1% IS. The following events will constitute 'treatment failure', and are based on the ELN criteria 2020 defining failure of a second line treatment adapted to include discontinuation of randomized treatment as an event:

- Twelve months (48 weeks) after the initiation of treatment BCR-ABL1 >1% IS
- Emergence of resistance mutations, high-risk ACA

For patients who have not reached treatment failure, their TTFs will be censored at the time of last study assessment (PCR, cytogenetic, hematologic or extramedullary) before the cut-off date.

TTF, PFS and OS will be estimated and graphically displayed using the K-M approach on FAS. The estimated rates by K-M method at various time points will be provided.

12.5.2 Safety endpoints

For all safety analyses, the safety set (SAF) will be used, except where stated otherwise.

Safety summaries (tables, figures) include only data from the on-treatment period with the exception of baseline data which will also be summarized where appropriate (e.g. change from baseline summaries). In addition, a separate summary for death including on treatment and post treatment deaths will be provided. In particular, summary tables for adverse events (AEs) will summarize only on-treatment events, with a start date during the on-treatment period (treatment-emergent AEs).

The overall observation period will be divided into three mutually exclusive segments:

1. Pre-treatment period: from day of participant's informed consent to the day before first dose of study medication
2. On-treatment period: from day of first dose of study medication to 30 days after last dose of study medication

3. Post-treatment period: starting at day 31 after last dose of study medication.

Adverse events

All the summary tables for adverse events (AEs) and deaths will be tabulated by randomized groups.

Summary tables for adverse events (AEs) will include only AEs that started or worsened during the on-treatment period, the *treatment-emergent* AEs. All information obtained on adverse events will be displayed by primary system organ class, preferred term and maximum severity.

The incidence of treatment-emergent adverse events (new or worsening from baseline) will be summarized, system organ class and/or preferred term, severity (based on CTCAE grades), type of adverse event, relation to study treatment.

Separate summaries will be provided for study medication related adverse events, death, serious adverse events, other significant adverse events leading to discontinuation, and adverse events leading to dose adjustment.

Serious adverse events, non-serious adverse events and adverse events of special interest (AESI) during the on-treatment period will be tabulated.

All deaths (on-treatment and post-treatment) will be summarized.

All AEs, deaths and serious adverse events (including those from the pre-treatment, on-treatment and post-treatment periods) will be listed and those collected before or after the on-treatment period will be flagged.

A participant with multiple adverse events within a primary system organ class is only counted once towards the total of the primary system organ class.

Adverse events of special interest (AESI) are defined as events (serious or non-serious) which are ones of scientific and medical concern specific to the sponsor's product or program, for which ongoing monitoring and rapid communication by the investigator to the sponsor may be appropriate. Such events may require further investigation in order to characterize and understand them.

Adverse events of special interest are defined on the basis of an ongoing review of the safety data. Selected AESIs are discussed in detail in the [Asciminib Investigator's Brochure].

The following will also be summarized both for a) **all** patients using combined sets (SAF and SAF 2), and for b) SAF 2 only:

- All deaths
- Serious adverse events and adverse events of special interest
- Adverse events lead to treatment discontinuation
- Grade 3 and 4 adverse events

Vital signs

All vital signs data will be summarized by visit/time.

12-lead ECG

ECGs (12-lead) including PR, QRS, QT, QTcF, and HR intervals will be obtained for each subject during the study. ECG data will be read and interpreted locally.

Categorical analysis of QT/QTc interval data based on the number of patients meeting or exceeding predefined limits in terms of absolute QT/QTc intervals or changes from baseline will be presented.

All ECG data will be summarized by visit/time.

Clinical laboratory evaluations

All laboratory data will be summarized by visit/time. Shift tables using the low/normal/high/ (low and high) classification will be used to compare baseline to the worst on-treatment value.

Grading of laboratory values will be assigned programmatically as per NCI Common Terminology Criteria for Adverse Events (CTCAE) version 5. The calculation of CTCAE grades will be based on the observed laboratory values only, clinical assessments will not be taken into account.

CTCAE Grade 0 will be assigned for all non-missing values not graded as 1 or higher. Grade 5 will not be used.

For laboratory tests where grades are not defined by CTCAE version 5.0, results will be categorized as low/normal/high based on laboratory normal ranges.

The following listings/summaries will be generated separately for hematology, and biochemistry tests:

- Listing of all laboratory data with values flagged to show the corresponding CTCAE version 5.0 if applicable and the classifications relative to the laboratory normal ranges

For laboratory tests where grades are defined by CTCAE version 5.0

- Worst post-baseline CTCAE grade (regardless of the baseline status). Each participant will be counted only once for the worst grade observed post-baseline.
- Shift tables using CTCAE version 5.0 grades to compare baseline to the worst on-treatment value

For laboratory tests where grades are not defined by CTCAE version 5.0:

- Shift tables using the low/normal/high/ (low and high) classification to compare baseline to the worst on-treatment value.

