If the event worsens the event should be reported a second time in the CRF noting the start date when the event worsens in toxicity. For grade 3 and 4 adverse events only, if improvement to a lower grade is determined a new entry for this event should be reported in the CRF noting the start date when the event improved from having been Grade 3 or Grade 4.

Conditions that were already present at the time of informed consent should be recorded in medical history of the participant.

Adverse events (including lab abnormalities that constitute AEs) should be described using a diagnosis whenever possible, rather than individual underlying signs and symptoms.

Adverse event monitoring should be continued for at least 30 days following the last dose of study treatment.

Once an adverse event is detected, it must be followed until its resolution or until it is judged to be permanent (e.g. continuing at the end of the study), and assessment must be made at each visit (or more frequently, if necessary) of any changes in severity, the suspected relationship to the interventions required to treat it, and the outcome.

Progression of malignancy (including loss of response, progression to accelerated phase or blast crisis and death due to disease progression) should not be reported as a serious adverse event, except if the investigator considers that progression of malignancy is related to study treatment.

Adverse events separate from the progression of malignancy (i.e. deep vein thrombosis at the time of progression or hemoptysis concurrent with finding of disease progression) will be reported as per usual guidelines used for such events with proper attribution regarding relatedness to the drug.

Information about adverse drug reactions for the investigational drug can be found in the Investigator's Brochure (IB).

Abnormal laboratory values or test results constitute adverse events only if they fulfill at least one of the following criteria:

- they induce clinical signs or symptoms
- they are considered clinically significant
- they require therapy

Clinically significant abnormal laboratory values or test results must be identified through a review of values outside of normal ranges/clinically notable ranges, significant changes from baseline or the previous visit, or values which are considered to be non-typical in participant with the underlying disease.

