2.7 Safety analyses

For all safety analyses, the Safety set (SAF, SAF 2) will be used, except where stated otherwise.

Safety summaries (tables, figures) include only data from the on-treatment period with the exception of baseline data which will also be summarized where appropriate (e.g. change from baseline summaries). In addition, a separate summary for death including on treatment and post treatment deaths will be provided. In particular, summary tables for adverse events (AEs) will summarize only on-treatment events, with a start date during the on-treatment period (treatment-emergent AEs).

The overall observation period will be divided into three mutually exclusive segments:

1. Pre-treatment period: from day of participant's informed consent to the day before first dose of study medication
2. On-treatment period: from day of first dose of study medication to 30 days after last dose of study medication
3. Post-treatment period: starting at day 31 after last dose of study medication.

The following will also be summarized for a) **all** subjects using combined sets (SAF and SAF 2), for b) SAF 2 only, for c) subjects by dose escalation status (with or without dose escalation) and for d) only for subjects with dose escalation (prior to and after dose escalation):

- All deaths
- Serious adverse events and adverse events of special interest
- Adverse events leading to treatment discontinuation
- Grade 3 and 4 adverse events

Analysis of ECG data, for dose escalation is mentioned in [section 2.7.4.1](#).

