2.7.1 Adverse events (AEs)

All the summary tables for adverse events (AEs) will be tabulated by randomized groups. AE summaries will include all AEs occurring during the on-treatment period. All AEs collected in the AE eCRF page will be listed along with the information collected on those AEs e.g. AE relationship to study drug, AE outcome, etc. AEs with start date outside of the on-treatment period will be flagged in the listings.

AEs will be summarized by number and percentage of subjects having at least one AE, having at least one AE in each primary system organ class (SOC) and for each preferred term (PT) using MedDRA coding. A subject with multiple occurrences of an AE will be counted only once in the respective AE category. A subject with multiple CTCAE grades or the same preferred term will be summarized under the maximum CTCAE grade recorded for the event. AE with missing CTCAE grade will be included in the 'All grades' column of the summary tables.

In AE summaries, the primary system organ class will be presented alphabetically and the preferred terms will be sorted within primary SOC in descending frequency. The sorting order for the preferred term will be based on their frequency in the asciminib 40 mg b.i.d. group.

The following adverse event summaries will be produced: overview of adverse events and deaths, AEs by SOC and PT, summarized by relationship, seriousness, leading to treatment discontinuation, leading to dose interruption/adjustment, requiring additional therapy, and leading to fatal outcome. The study treatment-related AEs/SAEs/AEs leading to treatment discontinuation as well as SAE with fatal outcome are summarized for the corresponding Safety set.

For posting to ClinTrial.gov and EudraCT, a summary table of on-treatment deaths and serious AEs and another summary table of non serious AEs, both including occurrences (an occurrence is defined as >1 day between start and prior end date of record of same preferred term) and sorted by SOC and PT, will be presented as well.

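### The SAP selects AEs by start date alone, so the re-entry made when a pre-treatment grade 3/4 AE partly improves on treatment counts as treatment-emergent, which two of the protocol's three statements do not intend.

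*Protocol*

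**What the plan says.** **Recording.** Protocol 10.1.1 has an AE entered again when it worsens, dated at the worsening. For grade 3 and 4 events only, it also asks for a second entry on improvement to a lower grade: "a new entry for this event should be reported in the CRF noting the start date when the event improved". Conditions already present at consent go to medical history. Protocol 8.2 and 8.4 send significant findings that begin or worsen after consent to the AE page.

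**Selection, protocol.** Section 12.5.2 makes three statements. The opening paragraph uses start date: "summary tables for adverse events (AEs) will summarize only on-treatment events, with a start date during the on-treatment period (treatment-emergent AEs"). Under the adverse events subheading it says: "Summary tables for adverse events (AEs) will include only AEs that started or worsened during the on-treatment period". Shortly after: "The incidence of treatment-emergent adverse events (new or worsening from baseline) will be summarized".

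**Selection, SAP.** Sections 2.1.1 and 2.7 repeat only the start-date rule. Section 2.7.1 adds that summaries take all AEs occurring in the on-treatment period, and that a subject counts once per category at the highest grade recorded. Neither of the protocol's other two statements is carried over. SAP section 4 records no change to the protocol's analyses.

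**Joining entries.** The only rule for contiguous entries concerns the registry posting tables in SAP 2.7.1: "an occurrence is defined as >1 day between start and prior end date of record of same preferred term". SAP 2.7 also plans selected safety tables "only for subjects with dose escalation (prior to and after dose escalation"), without saying how an event is allocated to one side or the other.

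**The concern.** The start-date rule does what is intended for worsening, because every worsening gets its own dated entry. It fails for improvement, because a partial improvement of a grade 3/4 event also gets its own dated entry. When the parent event began before first dose, the parent is left out of the tables and the improvement entry is kept. An AE that is getting better is then shown as one that emerged on asciminib.

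Safety and tolerability is the first-listed secondary objective, and many patients enter because of intolerance to their last TKI. An AE table that can count a declining event as a new one is undesirable even if few patients are involved. Two programmers working from the two documents could also produce different tables. The same ambiguity affects any analysis of time to first occurrence of an AE of special interest (SAP 2.7.1.1), where the clock could stop at the improvement date.

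**Working it through.** The documents give no figure to reproduce on this point. The check applies the two selection rules to the same AE histories. The dates are illustrative, not trial data, and day 1 is first dose.

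- Rule A (SAP 2.1.1 and 2.7): count an entry if it starts on or after day 1.
- Rule B (the new-or-worse-than-baseline statement in Protocol 12.5.2): count an entry if it starts on or after day 1 and its grade is above the grade at baseline.

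| History | Rule A | Rule B |
|---|---|---|
| Grade 3 from day -10, grade 2 from day 5 | counted, grade 2 | not counted |
| Grade 4 from day -10, grade 3 from day 5 | counted, grade 3 | not counted |
| Grade 3 from day -10, fully resolved on day 5 | not counted | not counted |
| Grade 2 from day -10, improving to grade 1 (no re-entry required) | not counted | not counted |
| Grade 2 from day -10, grade 3 from day 5 | counted, grade 3 | counted, grade 3 |
| Grade 2 from day -10, grade 3 from day 5, grade 2 from day 15 | counted, grade 3 | counted, grade 3 |

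The rules differ only in the first two rows: a grade 3/4 event open at first dose that falls to a lower grade without resolving. Only the second row reaches a grade 3/4 table.

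**Does once-per-category counting repair it?** It absorbs split entries when the parent is also on treatment, as in the last row. In the first two rows the parent is excluded by its start date, so the improvement entry is the only one left to count.

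**Does the posting-table rule repair it?** It is stated for those tables only. It also does not say which start date a joined occurrence takes, or whether joining comes before the on-treatment filter.

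**Size per affected patient**, at planned numbers, for a patient with no other on-treatment entry in that AE category:

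- SAF: 1/156 = 0.64 percentage points.
- SAF 2: 1/30 = 3.3 points. The protocol allows up to 30 patients, so the step is larger if fewer enrol.
- AE tables are by randomized group. Assuming an even split, the steps are 1/(156/2) = 1/78 = 1.3 points and 1/(30/2) = 1/15 = 6.7 points.

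The documents give no count of grade 3/4 events open at first dose, so no total can be computed.

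**The case against.** The strongest reply is that the protocol does not settle on the start-date rule. Two of its three statements, including the one limiting tables to AEs that started or worsened on treatment, point away from counting improvements, and SAP section 4 declares no departure. A careful programmer could follow them. That stands as a description of the protocol, and the plan should not be read as having decided to count recovery as toxicity. It does not rescue the SAP, whose operative text contains only the start-date rule. The started-or-worsened wording also does not fully decide the case, since an improvement entry has an on-treatment start date of its own. Only the comparison with baseline does.

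Several stronger readings are tempting but not supported:

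- **That resolving toxicity from the previous TKI is generally reported as an asciminib AE.** Complete resolution is an end date, not an entry. Toxicity present at consent is medical history unless it worsens. The platelet, bilirubin, lipase, electrolyte and QTcF limits, and the exclusion of severe or uncontrolled disease, narrow the route further.
- **That the tables before and after escalation to 200 mg are materially distorted.** Protocol 6.6.2 bars escalation after grade 3/4 toxicity possibly related to asciminib, and Table 6-4 generally requires permanent discontinuation for grade 4 non-hematologic reactions. Mainly unrelated events remain. SAP 2.7 also gives no allocation rule, so an error there is possible but not stated.
- **That main and posted AE tables will disagree.** The posting rule is too incomplete to say.

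The consequences are also limited. The study is non-comparative with no AE hypothesis, any error overstates toxicity, treatment-related summaries should be little affected, and the listings show every entry.

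**Conclusion.** The point holds in narrow form. Protocol 12.5.2 carries definitions of treatment-emergent that are not equivalent, and the SAP keeps only the one under which an improvement entry qualifies. As written, a grade 3/4 AE that began or worsened between consent and first dose, and partly improved on treatment, is counted as treatment-emergent at its lower grade.

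The size is 0.64 points per patient in SAF and 3.3 points in SAF 2, at planned numbers. The number of patients is unknown; that it is small is a judgement from the short window and the eligibility limits, not a derived figure. The error can only add AEs. The primary endpoint, its test and its power are unaffected. This is a minor correction, worth making because a stated rule gives a wrong count, not because the safety conclusions are in doubt.

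**What to change.** 1. **One definition.** In SAP 2.1.1, 2.7 and 2.7.1, and in the opening paragraph of Protocol 12.5.2, state that an AE is treatment-emergent if it is new on treatment, or if its grade on treatment exceeds its grade at baseline, meaning the last grade before first dose. The comparison should be with baseline, not with the preceding entry. A pre-treatment grade 4 event that goes on treatment to grade 2 and then grade 3 never exceeds baseline and should not count.
2. **Linkage.** Link each improvement entry to its parent event before the on-treatment filter is applied, for example by same preferred term and contiguous dates, and use the parent's start date. An improvement entry alone then never qualifies. If the posting-table gap rule is reused to find contiguous entries, add which start date governs.
3. **Escalation tables.** Allocate an event by the parent's start date, or to the period after escalation if it rises above its grade at escalation. Given the escalation criteria, this matters mainly for events unrelated to asciminib.

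The cost is SAP wording, a matching edit to one protocol paragraph, and one derivation on data already collected. No new data are needed.
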